6.12.2. Absolute Serum Creatinine ≥ 4.0 mg/dL or Estimated Creatinine Clearance <20 mL/min

If a subject experiences an absolute sCr ≥ 4.0 mg/dL or an eCrCl <20 mL/min at any time during the study, IP must be **temporarily interrupted**, and the subject will return to the site within 1 to 2 weeks (Retest 1) for a retest.

Baseline Through the Month 12 Study Visit

- From Baseline through the Month 12 study visit, if any retest eCrCl declines $\leq 15\%$ from Baseline and sCr <4.0 mg/dL and an eCrCl ≥ 20 mL/min, no further retests are required and the subject may restart IP, at the Investigator's discretion, and continue the protocol-scheduled visits. The re-initiation of IP may occur regardless of the duration of the interruption.

- If Retest 1 eCrCl declines >15% from Baseline or sCr \geq 4.0 mg/dL or an eCrCl <20 mL/min, the subject will return to the site for a retest approximately 3 to 4 weeks (Retest 2) after the initial decline was noted.
- If Retest 2 eCrCl declines >15% from Baseline or sCr \geq 4.0 mg/dL or an eCrCl <20 mL/min, the subject will return to the site for a retest approximately 7 to 8 weeks (Retest 3) after the initial decline was noted.
- After Retest 3, subjects should continue the protocol-scheduled visits. If eCrCl is \leq 15% of the Baseline and sCr <4.0 mg/dL and eCrCl \geq 20 mL/min, the subject may restart IP, at the Investigator's discretion.

Month 12 Study Visit to Month 24 Study Visit

- From the Month 12 study visit to the Month 24 study visit, Retests 2 (Weeks 3 to 4) and 3 (Weeks 7 to 8) should be performed if eCrCl declines >20% from Baseline or sCr \geq 4.0 mg/dL or eCrCl <20 mL/min.
- If any retest eCrCl declines \leq 20% from Baseline and sCr <4.0 mg/dL and an eCrCl \geq 20 mL/min, no further retests are required and the subject may restart IP, at the Investigator's discretion, and continue the protocol-scheduled visits. The re-initiation of IP may occur regardless of the duration of the interruption.

6.13. Management of Acute Gout Flares

If a subject experiences an acute gout flare, study medications, including gout flare prophylaxis, should continue uninterrupted. Gout flares should be treated aggressively as appropriate by the treating Healthcare Providers individualized to the subject and the clinical circumstances.

There are no current specific guidelines for the treatment of acute gout flares in patients with chronic kidney disease (CKD). Corticosteroids are often the preferred treatment option (alone or in combination, as applicable, with ongoing colchicine prophylaxis) for patients with CKD though dosages and administration (ie, oral or intra-articular) vary for individual patients (Curiel 2012, Gaffo 2008, El-Zawawy 2010). EULAR guidelines state that acute gout flares can be managed using intra-articular aspiration and injection of a long acting steroid, especially when safety or tolerability concerns limit the use of NSAIDs and colchicine (Zhang 2006).

Treatment with NSAIDs should generally be avoided (or used judiciously) for acute gout flares (Curiel 2012, Gaffo 2008, El-Zawawy 2010) and is not permitted for gout flare prophylaxis (Section 5.2.2).

6.14. Suspected Pregnancy (Exposure in Utero)

If a subject becomes pregnant, IP, XOI, and gout flare prophylaxis (if applicable) should be discontinued immediately. The Investigator or other site personnel must notify the Sponsor or designee of a pregnancy associated with IP exposure within 1 day; ie, immediately, but **no later than 24 hours**, after the Investigator becomes aware of it and record the event and the course of the pregnancy, including perinatal and neonatal outcome (when is known) on the Pregnancy Report Form that will be provided to each site. The same timelines apply when outcome information is available.

Pregnancy itself is not regarded as an AE unless there is a suspicion that the IP under study may have interfered with the effectiveness of a contraceptive medication. Congenital abnormalities/birth defects and spontaneous miscarriages should be reported and handled as SAEs. Elective abortions without complications should not be handled as AEs. The outcome of all pregnancies (spontaneous miscarriage, elective termination, ectopic pregnancy, normal birth, or congenital abnormality) should be followed up and documented even if the subject was withdrawn from the study. Partner pregnancy data may not be collected.

6.15. Overdose

An overdose is defined as a daily dose of IP more than 200 mg (>1 tablet).

AEs associated with an overdose should be recorded on the appropriate AE CRF; however, all overdoses, including those not associated with an AE, should be recorded on the appropriate CRF.

6.16. Premature Withdrawal From the Study

Subjects are free to withdraw from the study at any time without prejudice to further treatment. A subject who withdraws consent will always be asked about the reason(s) and the presence of any AE. The Investigator will follow up AEs outside of the clinical study. At the time of study withdrawal, subjects should complete the End of Study Visit. If a subject withdraws from participation in the study, then his/her enrollment/randomization code cannot be reused. Subjects who withdraw early from the study will not be replaced.

Possible reasons for early withdrawal of subjects from the study include the following:

- Subject withdraws consent
- Death
- Lost to follow up.

To ensure validity of study data, it is important to collect as much data as possible throughout the study. It is essential that Investigators maintain contact with the subjects. This contact will assist with subject retention and prevent missing data. Several approaches may be implemented to increase communication and retention (eg, telephone calls to the subject's emergency contact, emails, texts, offers of transportation arrangements, etc). Certain approaches must be approved by appropriate IRBs/ECs in compliance with local privacy laws/practices.

For subjects who withdraw early or do not have an End of Study Visit, the site or delegate should attempt to collect vital status information (dead or alive). Vital status, based on publicly available sources, may also be investigated at Month 24 for subjects who did not complete the study.

The date and the reason must be recorded on the CRF for all subjects who withdraw early from the study. See [Section 8.4.1](#) for End of Study Visit procedures.

7. STUDY RESTRICTIONS

7.1. Potential Drug Interactions

7.1.1. Interactions With Lesinurad

CYP2C9 Inhibitors, CYP2C9 Poor Metabolizers, and CYP2C9 Inducers

Lesinurad exposure is increased when it is co-administered with inhibitors of CYP2C9, and in CYP2C9 poor metabolizers. Lesinurad should be used with caution in patients taking moderate inhibitors of CYP2C9 (eg, fluconazole, amiodarone) and in CYP2C9 poor metabolizers.

Lesinurad exposure is decreased when lesinurad is coadministered with moderate inducers of CYP2C9 (eg, rifampin, carbamazepine), which may decrease the therapeutic effect of lesinurad.

CYP3A Substrates

In interaction studies with lesinurad and CYP3A substrates conducted in healthy subjects, lesinurad reduced the plasma concentrations of sildenafil and amlodipine. Although there was not a clinically significant interaction with atorvastatin, HMG-CoA reductase inhibitors that are sensitive CYP3A substrates may be affected. The possibility of reduced efficacy of concomitant drugs that are CYP3A substrates should be considered and their efficacy (eg, blood pressure and cholesterol levels) should be monitored.

Salicylates

Salicylates at doses higher than 325 mg per day may decrease the sUA lowering activity of lesinurad in combination with allopurinol. There are no restrictions for doses of salicylates of 325 mg or less per day (ie, for CV protection).

7.1.2. Interactions With Xanthine Oxidase Inhibitors

Investigators should be aware of potentially serious interactions when allopurinol and febuxostat are given in combination with other drugs. The following sections list the drugs that should not be administered or should be administered with caution (eg, may require dose adjustments or additional patient monitoring) with allopurinol and febuxostat according to the United States Product Insert (USPI) and/or the Summary of Product Characteristics (SmPC) ([Febuxostat 80 mg Tablets \[SmPC\] Rev December 2012](#), [Allopurinol \[US package insert\] Rev July 2015](#), [Allopurinol 100 mg Tablets \[SmPC\] Rev February 2013](#), [Uloric \[US package insert\] Rev March 2013](#)). Refer to the local product labels for complete information on drug interactions.

7.1.2.1. Allopurinol

Drugs that should not be administered or should be administered with caution while taking allopurinol include, but are not limited to, the following:

- 6-mercaptopurine
- azathioprine
- coumarin anticoagulants
- theophylline
- captopril
- ampicillin/amoxicillin
- cyclosporine
- didanosine
- vidarabine (adenine arabinoside)
- oxipurinol
- thiazide diuretics
- cyclophosphamide
- tolbutamide
- chlorpropamide

7.1.2.2. Interactions With Febuxostat

Febuxostat should not be administered with 6-mercaptopurine or azathioprine.

7.1.3. Interactions With Colchicine

Moderate or strong CYP3A inhibitors that should not be administered while taking colchicine prophylaxis include, but are not limited to, the following:

- atazanavir
- clarithromycin
- darunavir
- indinavir
- itraconazole
- ketoconazole
- lopinavir
- nefazodone
- nelfinavir
- ritonavir
- tipranavir
- saquinavir
- telithromycin
- amprenavir
- aprepitant
- diltiazem
- erythromycin
- fluconazole
- fosamprenavir
- verapamil

Inhibitors of P-gp that are prohibited while taking colchicine prophylaxis include, but are not limited to, the following:

- cyclosporine
- ranolazine

Potentially significant drug interactions have been reported between colchicine and HMG-CoA reductase inhibitors, other lipid-lowering drugs, and digitalis glycosides. Subjects receiving these medications are to be carefully monitored for any signs or symptoms of muscle pain, tenderness, or weakness, particularly during initial therapy with colchicine.

Refer to the local product label for complete information on drug interactions with colchicine or other gout flare prophylaxis medications (eg, prednisone, prednisolone, or their equivalent).

Subjects must discontinue colchicine for gout flare prophylaxis (expected through the Month 6 study visit) if inhibitors of P-gp or moderate or strong CYP3A inhibitors are administered while on colchicine. This includes intake of grapefruit or grapefruit juice.

Subjects who are randomized and who subsequently develop intolerance or toxicity to colchicine or need to take inhibitors of P-gp or moderate to strong CYP3A inhibitors prior to the Month 6 study visit should, when medically appropriate, switch to the alternate gout flare prophylaxis, low-dose oral corticosteroids for a short course, such as through the Month 3 study visit. If switching is not medically appropriate, randomized subjects may continue in the study without gout flare prophylaxis.

7.2. Food and Fluid Intake

All doses of study treatment should be taken with water. Subjects should be encouraged to stay well hydrated. Grapefruit juice, a moderate CYP3A inhibitor, should not be consumed if the subject is taking colchicine.

7.3. Subject Activity Restrictions

There are no special requirements or restrictions on activity level.

7.4. Contraception

Current data from nonclinical studies suggest that lesinurad is not a reproductive hazard and showed no evidence of a genotoxic risk to humans at the planned lesinurad dosing in this study (see lesinurad IB for more information). There are no available human data on use of lesinurad in pregnant women. As a precaution, female subjects of childbearing potential (including peri-menopausal women who had menstrual bleeding within 1 year) must use an effective non-hormonal method of birth control (see Study Reference Manual) while taking IP. Because of a potential for lesinurad to affect the efficacy of hormonal contraceptives, subjects using a hormonal contraceptive must also use an effective non-hormonal method of birth control.

Male study subjects and their partners are not required to use contraception during this study.

8. STUDY ACTIVITIES

This section lists study activities by study day or month. In this study, a month is defined as 28 days. Unless there is a safety concern, every effort should be made to avoid protocol deviations. Additional visits will be required if subjects experience changes in renal function as outlined in [Section 6.12](#).

During the Double-Blind Treatment Period, all visits will occur at the end of the study month (ie, the Month 3 Visit will occur on Day 84 [± 7 days]). All scheduled visits should be referenced back to the Baseline Visit.

See [Section 6](#) and the Study Reference Manual for detailed information on study procedures. See [Appendix A](#) for the schedule of events.

NOTE: subjects will be required to return to the site for additional visits if they have changes in renal function as outlined in [Section 6.12](#). At timepoints when there are multiple assessments, patient-reported outcomes (including SDS, WPAI:SHP, EQ-5D-3L), vital sign measurements, and ECG (if applicable) should be performed prior to other assessments, particularly prior to laboratory sample collections.

8.1. Screening Period (Day -28 to the Baseline Visit)

At the start of the Screening Period, prospective study subjects will be fully informed about the nature of the study and possible AEs. Subjects must read the ICF and sign the document after the Investigator has answered all questions to the subject's satisfaction. Further procedures can begin only after the consent form has been signed. Prospective subjects will be evaluated for entry into the study according to the eligibility criteria. The Investigator must evaluate the results of all examinations, clinical laboratory tests, and medical history to determine each subject's suitability for the study prior to randomization and starting IP.

8.1.1. Screening Visit 1 (Approximately 28 Days Before the Baseline Visit)

The following procedures and assessments will be performed:

- Obtain written informed consent.
- Review eligibility criteria.
- Record demographics.
- Record prior ULTs (including current XOI with dose) indicated for the treatment of gout.
- Take vital signs.
- Measure height and weight measurements and calculate BMI.
- Assess AEs (pretreatment events).
- Collect blood sample for the following serum chemistry analyses:
 - Analytes 1.

8.1.2. Screening Visit 2 (Within 3 Weeks After Screening Visit 1 [\pm 3 Days])

The following procedures and assessments will be performed:

- Review eligibility criteria (including a review of targeted medical history and concomitant medications).
- Take vital signs.
- Assess AEs (pretreatment events).
- Assess compliance with prescription XO1.
- Collect blood sample for the following serum chemistry analyses:
 - Analytes 1.
 - Human chorionic gonadotropin (HCG) pregnancy test for all females and follicle-stimulating hormone (FSH) test for females who report 12 months of spontaneous amenorrhea and are not surgically sterile.
- Collect urine sample for the following analysis:
 - Urinalysis.

8.1.3. Baseline Visit (4 to 7 Days After Screening Visit 2)

The following procedures and assessments will be performed:

- Review gout flare history prior to Screening and during the Screening period.
- Confirm continued eligibility.
- Record complete medical history.
- Record concomitant medications.
- Administer patient report outcome assessments.
- Take vital signs.
- Record 12-lead ECG.
- Assess AEs (pretreatment).
- Perform physical examination.
- Identify and measure target tophi.
- Collect blood sample for hematology.
- Collect blood sample for the following serum chemistry analyses:
 - Analytes 1.
 - Analytes 2.
 - Analytes 3.

- Collect blood sample for plasma biomarkers.
- Collect urine sample for the following analyses:
 - Urinalysis.
 - Protein-creatinine ratio.
 - Urine biomarkers.
- Assess compliance with prescription XOI and discontinue.
- Randomize subject.
- Dispense IP (lesinurad or placebo), XOI, and colchicine (if applicable).

8.2. Rescreening of Subjects

Subjects who fail to meet the eligibility requirements for the study may be rescreened up to 3 times, as appropriate, using a new screening number each time. The minimum time required before each rescreening is 1 month (28 days).

8.3. Treatment Period (Day 1 Through Month 24)

Subjects must meet all of the eligibility criteria listed in [Section 4.2](#) and [Section 4.3](#) before being randomized and starting IP, study-supplied XOI, and colchicine (as applicable). Subjects will receive IP in combination with an XOI for up to 24 months. Subjects who permanently discontinue IP early should complete an End of Treatment Visit ([Section 8.3.3](#)) as soon as possible after discontinuing IP, and a Post-End of Treatment Visit ([Section 8.4.1](#)) 1 month after the End of Treatment Visit, but should remain on the study and follow the protocol-scheduled visits.

8.3.1. Day 1 (1 Day After Baseline Visit)

This is not a study visit. Subjects will receive study-supplied medications (IP, XOI, and colchicine, as applicable) at their Baseline Visit and will start taking these medications at home on Day 1 (1 day after Baseline Visit). Colchicine may be taken at Baseline. All study-supplied medications should be taken in the morning. Refer to [Section 5.3](#) for details on administration of study-supplied medications.

8.3.2. Month 1 (Day 28 ±7 Days) and Months 3 Through 21 (Visits Every 3 Months ±7 Days)

The following procedures and assessments will be performed at each visit, except where otherwise noted:

- Administer patient-reported outcome assessments (except at Month 1).
- Review gout flares that occurred since the last study visit.
- Take vital signs.
- Assess AEs.
- Record concomitant medications.

- Assess compliance with IP (lesinurad/placebo).
- Assess compliance with XO1.
- Assess compliance with gout flare prophylaxis (Months 1, 3, and 6).
- Measure target tophi (Months 6, 12, 18).
- Collect blood sample for hematology (Months 6, 12, and 18).
- Collect blood sample for the following serum chemistry analyses:
 - Analytes 1.
 - Analytes 2.
 - Analytes 3 (Months 6, 12, and 18).
 - Pregnancy test for women of childbearing potential (Month 12).
- Collect blood sample for plasma biomarkers (Months 6, 12, and 18).
- Collect urine sample for the following analyses:
 - Urinalysis.
 - Protein-creatinine ratio (Months 6, 12, and 18).
 - Urine biomarkers (Months 6, 12, and 18).
- Except at Month 1, dispense IP (lesinurad or placebo), XO1, and colchicine (as needed at Month 3).

For subjects that have permanently discontinued IP, maintaining the visit schedule is recommended. Although all assessments are encouraged, at a minimum, it is requested that collection of AEs and collection of a blood sample for Analytes 1 occur.

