3.2.3. Exploratory Endpoints

- Percent change from Baseline in the sum of the areas of all target tophi at scheduled visits, among subjects with ≥ 1 target tophus at Baseline.
- Proportion of subjects who experienced complete resolution of at least 1 target tophus at any time during study, among subjects with ≥ 1 target tophus at Baseline.
- Functional impairment assessed employing the Sheehan Disability Scale (SDS; individual domains as well as total functional impairment) at last on-study visit.
- Work productivity as assessed employing the Work Productivity and Activity Questionnaire: Specific Health Problem (WPAI:SHP; absenteeism, presenteeism, work productivity loss, and activity impairment) at last on-study visit.
- Health status as assessed employing the EuroQol Five Dimensions Questionnaire 3 level (EQ-5D-3L; both descriptive system and visual analogue scale) at last on-study visit.
- Proportion of subjects with gout flares at each 3-month interval during the study period.

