Subjects who permanently discontinue IP early should complete an End of Treatment Visit (Section 8.3.3) as soon as possible followed by a Post-End of Treatment Visit (Section 8.4.1) 1 month after the End of Treatment Visit. Subjects should then continue on study and follow the protocol-defined schedule of events, through Month 24. The subject has the option to continue on study-supplied XOI during this time. Although all assessments are encouraged, at a minimum, it is requested that collection of AEs and collection of a blood sample for Analytes 1 (see Table 1) occur. Alternatively, if the subject does not agree to this option, a modified follow-up including, eg, regular telephone contacts or a contact at Month 24, should be arranged, if agreed to by the subject and in compliance with local data privacy laws/practices. Subjects who do not wish to continue on study after discontinuing IP should complete an End of Study Visit (Section 8.4.2) 1 month after treatment discontinuation.

If IP is permanently discontinued prior to the Month 6 study visit, then gout flare prophylaxis should also be discontinued.

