6.10.4. Gout Flares

Acute gout flares occur when monosodium urate crystals in the joint(s) cause acute inflammation. A flare is characterized by pain, redness, swelling, and warmth lasting days to weeks. Pain may be mild or excruciating. Most initial attacks occur in lower extremities. The typical presentation in the metatarsophalangeal joint of the great toe (podagra) is the presenting joint for 50% of people with gout (<http://www.cdc.gov/arthritis/basics/gout.html>, accessed 6 October 2016).

Gout flares will be recorded on the CRF, including information regarding the start and stop date; patient-reported severity (mild/moderate/severe); and the treatment that was required, if any. Medications used for gout flare treatment will be documented on the concomitant medications CRF.

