6.11. Adverse Events

6.11.1. Adverse Event Definition

An AE is the development of an undesirable medical condition or the deterioration of a pre-existing medical condition following or during exposure to a pharmaceutical product, whether or not considered causally related to the product. An undesirable medical condition can be symptoms (eg, nausea, chest pain), signs (eg, tachycardia, enlarged liver), or the abnormal results of an investigation (eg, laboratory findings, electrocardiogram). In clinical studies, an AE can include an undesirable medical condition occurring at any time, including the screening period, even if no study treatment has been administered.

Gout flares will not be captured on the AE form. New tophi or enlarging tophi that are not clinically adverse will not be captured on the AE form. However, gout flares or changes in tophi that meet the definition of an SAE must be reported as an SAE ([Section 6.11.6](#)).

If deterioration in a laboratory value/vital sign is associated with clinical signs and symptoms, the sign or symptom will be reported as an AE and the associated laboratory result/vital sign will be considered as additional information. Wherever possible, the reporting Investigator uses the clinical rather than the laboratory term (eg, anemia versus low hemoglobin value). In the absence of clinical signs or symptoms, clinically-relevant deteriorations should be reported as AE(s).

Protocol-mandated permanent discontinuation of IP per the sCr/eCrCl criteria described in [Section 5.3.2.1.1](#) should be reported as an AE. Additional CRFs will be completed for any mandated sCr retests ([Section 6.12](#)) and for certain diagnostic tests.

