9.4.4. Exploratory Endpoints

For all exploratory endpoints, descriptive statistics will be provided at each scheduled visit.

For percent change from Baseline in the sum of target tophi area among subjects with target tophus at Baseline, the between-treatment difference will be assessed using similar MMRM analysis as appropriate as in [Section 9.4.2.1](#).

For the proportion of subjects with target tophi at Baseline who experience complete resolution of at least 1 target tophus at any time during study, the between-treatment difference in tophus resolution rates in this subset of subjects will be assessed using the CMH test statistic, stratified by type of XOI, and Screening eCrCl (as appropriate as stated in [Section 9.1](#)). Results will be summarized by randomized treatment group and expressed as proportions and corresponding adjusted 95% CI of the difference between response rates.

The proportion of subjects reporting gout flares will also be summarized at each visit.

The patient-reported outcomes (ie, SDS, WPAI:SHP, and EQ-5D-3L) will be summarized by visit (Visits 3, 6, 9, . . . 24). In addition, the mean score at last on-study visit will be analyzed using analysis of covariance (ANCOVA), which include terms for treatment stratification factors (as appropriate as stated in [Section 9.1](#)) and Baseline patient reported outcome value as covariate.

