Note: A clinical month is considered to be 28 days. All scheduled visits should be referenced to the Baseline Visit. See [Section 6](#) for more information on study procedures and assessments. Additional visits will be required if subjects experience changes in renal function as outlined in [Section 6.12](#).

^a The visit window during the Double-Blind Treatment Period is ± 7 -days beginning with the Month 1 Visit.

^b Subjects who permanently discontinue IP early but remain on study should complete a Post-End of Treatment Visit approximately 28 days after the End of Treatment Visit.

^c All subjects should complete an End of Study Visit approximately 28 days after completing the Treatment Period or withdrawing early from the study.

^d For subjects who have permanently discontinued IP, at a minimum AE should be assessed and blood drawn for Analyte panel 1.

^e Investigator must confirm eligibility prior to randomization.

^f Baseline assessment is an assessment of gout flare history and post-Baseline assessment is an assessment of gout flares since the last visit.

^g The estimated creatinine clearance (eCrCl) for each Screening Visit and the average of both Screening Visits (the "Screening eCrCl") will be calculated by the Cockcroft-Gault formula using ideal body weight.

^h The follicle-stimulating hormone (FSH) test will be done at SV2 only, and only for females with 12 months of spontaneous amenorrhea who are not surgically sterile. The human chorionic gonadotropin (HCG) test will be done at SV2 for all females and again at Month 12 for all females except those who are surgically sterile or not of childbearing potential as confirmed by the SV2 FSH.

ⁱ Includes assessment of protein by dipstick by the central laboratory.

^j After a subject permanently discontinues IP, dispensing and compliance are not required.

^k Colchicine will be dispensed at Baseline Visit and Month 3 Visit as applicable.

^l Prescription XO compliance will be assessed from Screening to Baseline. Study-supplied XO compliance will be assessed from Day 1 through Month 25/End of Study.

^m Corticosteroids for gout flare prophylaxis may be taken through Month 3.

APPENDIX B. ACTIONS REQUIRED IN CASES OF INCREASES IN LIVER BIOCHEMISTRY AND EVALUATION OF HY'S LAW

1. Introduction

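### The minimum follow-up after IP stops omits the gout flare review, so non-serious flares can go unascertained in later intervals, and no denominator rule covers those intervals

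*Combined protocol and SAP*

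**What the plan says.** **Off-IP minimum.** Subjects who permanently stop IP are asked to stay on the visit schedule through Month 24. Protocol Section 8.3.2 encourages every assessment at those visits but adds that "at a minimum, it is requested that collection of AEs and collection of a blood sample for Analytes 1 occur". Section 5.3.2.1.2 sets the same floor. Appendix A repeats it in footnote d: "at a minimum AE should be assessed and blood drawn for Analyte panel 1". In the schedule, that footnote is attached to the AE and Analytes 1 rows for Months 1 to 21, not to the gout flare row. For subjects who decline visits, Sections 5.3.2.1.2 and 8.4 allow modified follow-up, such as regular telephone calls or one contact at Month 24. Neither section says what is to be asked.

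**Flares and the AE form.** Section 6.11.1 states: "Gout flares will not be captured on the AE form". It makes one exception: "gout flares or changes in tophi that meet the definition of an SAE must be reported as an SAE". Section 6.10.4 sends flares to the CRF and adds: "Medications used for gout flare treatment will be documented on the concomitant medications CRF". That concomitant medication record is also outside the off-IP minimum.

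**Endpoint and analysis.** The exploratory endpoint in Section 3.2.3 is: "Proportion of subjects with gout flares at each 3-month interval during the study period". Section 9.4.4 says only: "The proportion of subjects reporting gout flares will also be summarized at each visit".

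**The concern.** The endpoint needs to know, for each subject and each 3-month interval, whether a flare occurred. For subjects off IP, the stated minimum contains neither of the two routine places where a non-serious flare would show up: the flare review and the concomitant medication record. The one record of clinical events that it does contain, the AE form, is closed to non-serious flares.

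A site can therefore meet the stated minimum without asking about flares. The analysis text does not say whether a subject who was not asked is missing or flare-free for that interval. The sUA responder endpoint, by contrast, has an explicit rule for missing results (Section 9.4.3).

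At stake is the accuracy of the flare proportions, increasingly so at later intervals as more subjects come off IP. The unasked subjects may not be a random sample. Under Section 5.3.2.1.2, those who stop IP before Month 6 also stop flare prophylaxis, and some stop IP because they have stopped the XOI or started another urate-lowering drug.

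**Working it through.** The documents give no flare rate, IP discontinuation rate, or share of subjects on minimum follow-up, so the plan has no figure to reproduce for this endpoint. The check has two parts.

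**1. Which intervals lose their flare review?** Take an assumed subject who stops IP at Month 7 and then attends visits on the minimum only.

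- End of Treatment Visit, about Month 7: flare review listed without qualification (Section 8.3.3).
- Post-End of Treatment Visit, about Month 8: flare review listed, looking back to the last study visit (Section 8.4.1).
- Months 9, 12, 15, 18 and 21: AEs and Analytes 1 suffice, so no flare review is required.
- Month 24: unclear. Section 5.3.2.1.2 applies the minimum through Month 24, but footnote d is not on the Month 24 column of Appendix A.
- End of Study Visit, about Month 25: flare review listed, again only back to the last study visit (Section 8.4.2).

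The four intervals from Month 9 to Month 21 have no flare review. Months 6 to 9 are covered only up to Month 8. Months 21 to 24 depend on how the Month 24 visit is read. The End of Study look-back does not reach the gap, because the minimum-only visits count as study visits.

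A subject followed only by telephone who then attends the End of Study Visit is different. The last study visit was at about Month 8, so the look-back spans 25 − 8 = 17 months and relies on recall.

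**2. How large would the effect be if unasked subjects were counted as flare-free?** Let m be the share of the arm with no flare review in an interval, a the flare proportion among reviewed subjects, and u the proportion among unreviewed subjects. All are assumptions, and all flares are treated as non-serious.

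- True proportion = (1 − m)·a + m·u
- Reported with the whole arm as denominator = (1 − m)·a, a shortfall of m·u
- Reported with only reviewed subjects as denominator = a

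With a = u = 20%, the true value is 20% and the whole-arm figure is 20% × (1 − m):

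| m | Reported |
|---|---|
| 5% | 19% |
| 10% | 18% |
| 20% | 16% |
| 30% | 14% |

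**Between arms.** The false difference is the difference in m·u. With m and u equal in both arms it is zero. With u = a = 20% and m = 20% on lesinurad versus 10% on placebo, the table shows 16% versus 18%, a false difference of −2.0 points (z about −0.65 at 300 per arm). With m = 30% versus 15% it shows 14% versus 17%, or −3.0 points (z about −1.0). Swapping the shares reverses the sign.

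**Limit of restricting the denominator.** If unreviewed subjects flare more often, say u = 30% with a = 20% and m = 10%, the truth is 0.9 × 20% + 0.1 × 30% = 21%. The whole-arm figure is 18% and the reviewed-only figure is 20%. The restriction removes most of the error but not all, so asking the question matters more than the choice of denominator.

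**The case against.** Several points on the other side stand.

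- Section 11.6.3 lists all gout flare events, with dates and severity, among the minimum source data for each subject and does not exempt those off IP. Section 6.10.4 is not limited to on-IP time either. This is a duty to record flares that come to light. It does not put the flare question into the minimum visit, so the sections are out of step.
- A reader might infer that subjects off IP have no flare ascertainment at all. The documents do not support that. Serious flares must be reported as SAEs, all assessments are encouraged at every visit, and flare review is listed without qualification at the End of Treatment, Post-End of Treatment and End of Study Visits.
- A reader might also infer that unasked subjects count as flare-free. That is a plausible default but is not stated. The all-subjects denominator in Section 9.4.2.2 is written for renal outcomes. Sections 9.4.2.3 and 9.4.2.4 adopt that method expressly, and Section 9.4.4 does not. Section 9 also leaves further detail to an SAP.
- A third tempting reading is that the gap favours lesinurad. No document figure shows unequal stopping or unequal use of minimum follow-up, and Section 1.2.1 describes the AE profile of the combination as similar to that of an XOI alone. Renal reactions identified for lesinurad make unequal stopping possible but do not establish it.
- A light minimum helps to retain subjects who might otherwise withdraw. That is a fair reason for a short list, but one more question adds little to it.

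**Conclusion.** The gap is real but limited. It concerns non-serious flares at off-IP visits between the Post-End of Treatment and End of Study Visits, and modified follow-up for which no flare question is named. The missing denominator rule leaves open how those intervals enter the proportions.

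If unasked subjects are counted as flare-free and flare at the same rate as the others, the proportion falls short by the unascertained share in relative terms. That is 2 points at a 10% share and 4 points at a 20% share, for an assumed true 20%. The documents settle neither whether the arms would be biased against each other nor in which direction.

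The endpoint is exploratory and its summary is descriptive. The eCrCl and sUA analyses are untouched, since Analytes 1 includes creatinine and uric acid. This is a cheap improvement, not a threat to the study's main conclusions. It has to be made prospectively, because flares not asked about at the time cannot be recovered reliably.

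**What to change.** 1. Add a review of gout flares since the last contact, recorded on the flare CRF, to the off-IP minimum in Sections 5.3.2.1.2 and 8.3.2.
2. Make the same addition to Appendix A footnote d, and attach that footnote to the gout flare row as well.
3. Name the same question in the modified follow-up by telephone or Month 24 contact (Sections 5.3.2.1.2 and 8.4).
4. In Section 9.4.4, define each 3-month interval's denominator as the subjects whose flare review covers that interval, and report that number by arm.

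The cost is one more question at contacts already planned, a footnote edit and a sentence on the denominator. No visit, sample or procedure is added.
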